4.2.4 Per Protocol population (PP)

All randomized patients from the ITT population without any major protocol deviations.

The exact definition of major protocol deviations will be discussed with the clinical team case by case during the review of the data and will be described in the Data Review Report.

The primary efficacy variable will be analysed on the PP.

In case an error occurs in treatment allocation, the following rule will be followed: if a patient was randomised but received the incorrect treatment, he/she will be reported under his/her randomised treatment group for all analyses performed on the ITT population, but he/she will be reported under the treatment actually received for all analyses performed on the safety population. The patient will be excluded from the PP population.

4.3 Sub-group analyses

The following subgroup will be defined:

Forms			
Title		Statistical Analysis Plan Template	
Code		Version	Effective Date
FRM_ST03_032		02	02 Oct 2017
		12 of 26	

- Patients treated with triple therapy: subjects who were treated with “LAMA+LABA” or “LAMA+LABA+ICS”. Considering that LABD category of treatments can be subdivided in “LAMA”, “LABA” or “LABA+LAMA”, this subgroup will be selected. Other subgroup analyses may be performed during post-hoc analyses for efficacy and safety endpoints based on baseline disease characteristics which could provide evidence to assess effectiveness, adherence levels and the true value of adding ICS treatment to LABD.

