2.2. Background

For GOLD D patients, GOLD recommends LABD either alone (LAMA or LABA) or in combination (LAMA+LABA), mainly to reduce symptoms and exacerbations (Wedzicha et al 2016). GOLD also recommends adding ICS to LABD, but only if patients are young and/or have eosinophilia and/or a history of asthma, mainly because LABA+ICS is the most prescribed treatment in these patients.

We speculate that multimorbid elderly COPD patients recently hospitalized with an AECOPD and concomitant cardiovascular disease may have fewer re-hospitalizations and increased survival in the following year if treated with LABD+ICS rather than with LABD alone.

In this study patients will be randomised to one of two treatment regimens:

- 1) Usual and optimized treatment for concomitant chronic diseases plus LABD(s) but no ICS
- 2) Usual and optimized treatment for concomitant chronic diseases plus LABD(s)+ICS.

The choice of the particular LABD(s); (1 or 2) and ICS will be left to the discretion of the clinical investigator. Thus, the proposed study will be a real-life but randomized study with a 12 month treatment period followed by 3 months follow-up. All diagnostic procedures and medical treatments will be performed according to best medical practice (Percorsi Diagnostico Terapeutici Assistenziali (PDTA)) at the study centre. Best medical practice is usually based on the most recent and credited international guidelines for these chronic diseases such as the ESC guidelines for cardiac diseases (www.esc.org) and GOLD guidelines (www.goldcopd.org) for COPD.

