6.1. Study Intervention(s) Administered

In this study patients will be randomised to receive one of the following two treatment regimens for up to 12 months:

- 1) Usual and optimized treatment for concomitant cardiovascular (CV) diseases plus inhaled long acting bronchodilator(s) (LABD(s))
- 2) Usual and optimized treatment for concomitant CV diseases plus inhaled long acting bronchodilator(s) and inhaled glucocorticosteroids (ICS).

The choice of the specific LABD(s) and/or ICS for each patient will be left to the discretion of the clinical investigator. All treatments will be administered at licensed dosages. During the study, the doses of all medications may be adjusted by the investigator according to licensed dosages. Both study groups will receive prescriptions for study medication, which will be collected by the patients from their local pharmacy or hospital pharmacy department. Prescription data will be captured on the electronic case report form (eCRF).

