6.3. Measures to Minimize Bias: Randomization and Blinding

All participants will be centrally assigned to randomized study intervention using an Interactive Web Response System (IWRS). Before the study is initiated, the log in information and instructions for the IWRS will be provided to each site.

The center will be considered as a unique stratifying factor, so the randomization will follow a balanced-block center-stratified design.

Study intervention will be dispensed at the study visits summarized in the SoA.

This is an open-label study; however, the specific intervention to be taken by a participant will be assigned using an IWRS. The site will contact the IWRS prior to the start of study intervention

administration for each participant. The site will record the intervention assignment on the applicable case report form.

Potential bias will be reduced by using central randomization.

Since this is an open label study, no unblinding procedures are foreseen.

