7.1. Discontinuation of Study Intervention

Participants who are hospitalized during the study period will be allowed to continue in the study until the end at the discretion of the principal investigator and/or the participant. The investigator/participant can decide to discontinue the study drug for safety or efficacy reasons.

Albeit we will invite patients and doctors to stick to the initial treatment unless required by changed medical condition, the specific COPD treatment regimen (LABD(s) without ICS or LABD(s) + ICS) can be changed at any point during the study. Treatment with ICS in the only LABDs group will be permitted if, on clinical Investigators judgement, it would be necessary for patient temporary conditions for at maximum 15 days in case of patient treated at home or for 15 days (at maximum) after hospital discharge in case of hospitalised patient. If the ICS treatment will surpass these periods, the patient will be considered being switched to the LABD + ICS group and considered as protocol violator.

See the SoA for data to be collected at the time of intervention discontinuation and follow-up and for any further evaluations that need to be completed.

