9.4.8. Other Analyses

A subgroup analysis will be performed by considering the patients randomized with Triple Therapy (LAMA+LABA+ICS) or LAMA+LABA. The analysis of primary endpoint and the number of re-hospitalizations and deaths (all cause) secondary analysis will be performed on this subset of patients.

Other subgroup analyses may be performed for efficacy and safety endpoints based on baseline disease characteristics which could provide evidence to assess effectiveness, adherence levels and the true value of adding ICS treatment to LABD.

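### The LAMA+LABA / triple-therapy subgroup is defined by treatment received, with no time point, so its comparison of arms is not protected by randomisation

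*SAP*

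**What the plan says.** **What is randomised.** Protocol 6.1: "In this study patients will be randomised to receive one of the following two treatment regimens for up to 12 months", namely cardiovascular treatment plus LABD(s), or the same plus ICS. Protocol 6.3: "The center will be considered as a unique stratifying factor, so the randomization will follow a balanced-block center-stratified design". It is open label, and the IWRS assigns the arm.

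**What is not randomised.** Protocol 6.1: "The choice of the specific LABD(s) and/or ICS for each patient will be left to the discretion of the clinical investigator". Protocol 2.2 makes clear that this includes the number of bronchodilators: "The choice of the particular LABD(s); (1 or 2) and ICS will be left to the discretion of the clinical investigator".

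**The subgroup.** Protocol 9.4.8: "A subgroup analysis will be performed by considering the patients randomized with Triple Therapy (LAMA+LABA+ICS) or LAMA+LABA". SAP 4.3 instead has "Patients treated with triple therapy: subjects who were treated with" LAMA+LABA or LAMA+LABA+ICS. It does not say whether first prescription, any use or longest use counts. SAP 4.8, which lists changes from the protocol, does not mention this one.

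**The analyses.** SAP 7.1 repeats the primary-endpoint analyses in the subgroup: Kaplan-Meier, log-rank stratified by centre, and Cox with centre, age and treatment. Protocol 9.4.8 also repeats the count of re-hospitalisations and deaths there; SAP 7.2 does not mention the subgroup. Neither document attaches a caveat about selection.

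**The concern.** A subgroup keeps the protection of randomisation when membership is settled before allocation, or cannot be influenced by it. Here membership rests on a prescribing decision that may be taken with the arm known. The protocol's Introduction suggests why the decision could differ by arm: it reports that guidelines reserve triple therapy for patients in whom other options are insufficient, but treat LAMA+LABA as an ordinary option for the same severity group. A second bronchodilator could then mark harder-to-treat disease in the ICS arm and routine care in the LABD arm.

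The missing time point adds a second route. If any use counts, a patient given a second bronchodilator after a first re-hospitalisation enters the subgroup because of the outcome being analysed.

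At stake is the interpretation of the only subgroup the plan names. If the two arms' members differ in underlying risk, the subgroup hazard ratio can show an ICS effect that is absent or hide one that is present.

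**Working it through.** **1. The plan's own figure.** The documents give no size or power for the subgroup. The whole-trial figure of 464 per group reproduces (protocol 9.2, SAP 3.3):

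- HR = ln(0.91)/ln(0.85) = 0.580.
- Freedman events, two-sided 5%, 80% power: 7.849 × (1.580/0.420)² ≈ 112.
- Per group: 112/(0.15 + 0.09) = 467, within 3 of 464. Power at 464 per group is 80.0%.

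So 464 per arm and a 15% risk are used below where a scale is needed.

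**2. Can membership depend on the arm?**

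- The number of bronchodilators is discretionary (protocol 2.2, 6.1) and is not a stratification factor (6.3).
- Protocol section 8, Visit 2, describes randomisation and then prescriptions. The site contacts the IWRS before treatment starts (6.3). No step requires the intended bronchodilators to be recorded first.
- The default Cox model has no baseline severity measure (SAP 4.4), and the log-rank test is stratified by centre only.

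The plan therefore permits arm-dependent membership and does not correct for it by default.

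**3. How large could the distortion be?** Every selection rate below is an assumption; none comes from the documents. There is no true ICS effect. With high-risk share h, selection rates s_H and s_L, and risks p_H and p_L:

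subgroup risk = [h·s_H·p_H + (1−h)·s_L·p_L] / [h·s_H + (1−h)·s_L]

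*Pattern A: triple therapy goes mainly to sicker patients.* h = 0.4. The ICS arm selects 90% of high-risk and 30% of low-risk patients; the LABD arm selects 90% and 80%. Risk is in units of p_L.

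- p_H = 2p_L: ICS (0.72 + 0.18)/0.54 = 1.667; LABD (0.72 + 0.48)/0.84 = 1.429; risk ratio 1.17.
- p_H = 3p_L: ICS (1.08 + 0.18)/0.54 = 2.333; LABD (1.08 + 0.48)/0.84 = 1.857; risk ratio 1.26.

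*Pattern B: LAMA+LABA goes mainly to sicker patients in the LABD arm.* h = 0.5, p_L = 10%, p_H = 20% (15% overall). Each arm contributes 60% of 464, or 278 patients. HR = ln(1 − p_ICS)/ln(1 − p_LABD). Rejection is for a two-sided 5% test of two proportions, used as a stand-in for the log-rank test.

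| LABD low/high selected | ICS low/high selected | Risk LABD | Risk ICS | Null HR | Rejection |
|---|---|---|---|---|---|
| 60%/60% | 60%/60% | 15.0% | 15.0% | 1.00 | 5.0% |
| 50%/70% | 60%/60% | 15.8% | 15.0% | 0.94 | 5.9% |
| 40%/80% | 60%/60% | 16.7% | 15.0% | 0.89 | 8.4% |
| 40%/80% | 70%/50% | 16.7% | 14.2% | 0.84 | 12.9% |

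Last row: LABD (0.02 + 0.08)/0.6 = 16.67%; ICS (0.035 + 0.05)/0.6 = 14.17%; HR = 0.1528/0.1823 = 0.84.

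**4. Range.** Pattern A gives risk ratios and pattern B hazard ratios. On the risk-ratio scale the last row is 14.17/16.67 = 0.85, so the span is about 0.85 to 1.26. The first row shows no bias when selection is unrelated to risk in both arms.

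**The case against.** Several stronger readings are tempting, and the documents do not support them.

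- **That investigators choose the bronchodilators knowing the arm.** This is inferred from the order of events at Visit 2. No text says when the choice is made, and Visit 1 already allows medication to be reviewed and updated. What stands is that nothing prevents it.
- **That protocol 7.1 lets the number of bronchodilators change at will.** The regimen that "can be changed at any point during the study" is there specified as LABD(s) without ICS or LABD(s)+ICS, so the passage concerns ICS crossover. Protocol 6.6 concerns doses within the arm. Visits 3 to 5 provide for COPD treatment to be reviewed and updated, which leaves room for a change in number without stating it.
- **That triple therapy in one arm and dual in the other is itself a fault.** It is the intended ICS contrast. Bias needs selection that differs by arm and is related to risk.
- **That the bias has a known sign or size.** Patterns A and B point in opposite directions. Pattern A also implies about 251 ICS against 390 LABD patients (54% and 84% of 464), an imbalance that a table of subgroup numbers would reveal. Pattern B has equal numbers and would pass that check.
- **That the trial's conclusion rests on this analysis.** Success is declared from the primary log-rank test in the ITT population. The subgroup carries no decision rule, and neither document presents it as the decisive test of adding ICS to LAMA+LABA.

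In the plan's favour, other confounders may be added to the Cox model at Data Review. That is discretionary, names no severity measure and leaves the log-rank test unchanged.

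**Conclusion.** The point holds as a defect of definition. Following SAP 4.3 as written gives a subgroup whose membership can depend on the allocated arm and, for want of a time point, on events after allocation. Its hazard ratio should not be presented as a randomised comparison.

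The direction and size of any bias are unknown. The ratios of about 0.84 to 1.26 under no effect show only what assumed selection patterns could produce; they are not estimates for this trial. A reader might infer that selection by arm has been shown, or that the primary result is compromised. Neither follows: the plan permits such selection but does not demonstrate it, and the primary ITT log-rank test does not use the subgroup.

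Two smaller points are certain from the text. The protocol's wording describes a randomisation that does not take place. The SAP's triple-therapy label also covers LABD-arm patients who are in the subgroup because they receive LAMA+LABA without ICS.

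**What to change.** 1. **Fix the time point.** Define membership at a stated time no later than the first Visit 2 prescription, ignore later treatment changes, and analyse by randomised arm. This closes the route through later events. It does not remove dependence on the arm if that prescription is written after allocation.
2. **Add a pre-randomisation version.** Define it by COPD maintenance therapy recorded before randomisation: LAMA+LABA, with or without ICS. Report it separately by prior ICS use, because prior ICS users allocated to LABD form a withdrawal comparison, whereas prior LAMA+LABA users allocated to LABD+ICS form an addition comparison. The data should exist: Visit 1 records COPD history and related treatment, and protocol 6.5 requires names and dates of medication taken at enrolment.
3. **Label and adjust the prescription-based version.** Call it non-randomised, show subgroup numbers and baseline characteristics by arm, and adjust its Cox model for prespecified severity measures already collected, such as FEV1, CAT, prior-year exacerbations and cardiac comorbidity.
4. **Reconcile the documents.** Align protocol 9.4.8 with SAP 4.3 and 7.1, state whether the re-hospitalisation and death count is repeated in the subgroup, record the change in SAP 4.8, and rename the subgroup.

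The cost is SAP wording, a few derivations and extra tables, with no new data collection. The downside is that the pre-randomisation subgroup may be smaller than, or differ from, the regimens later prescribed. Inclusion criterion 3 admits patients treated only with short-acting bronchodilators, and treatment is to be optimised at study start. Splitting by prior ICS use reduces the numbers further. This version answers a slightly different question, and the SAP should say so.

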4.4 Covariates

All the analysis of covariance (ANCOVA) models will include the baseline value of the variable and age as quantitative independent variables, treatment group and centre as qualitative independent variables.

The Poisson regression model and the Cox proportional hazards model will include center and treatment group as qualitative independent variables and age as quantitative independent variable.

The baseline to be considered in the statistical analysis for each variable is reported in the table below:

Endpoint	Baseline
Spirometry	Visit 2 (randomization)
COPD Assessment test (CAT)	Visit 2 (randomization)
mMRC dyspnea scale	Visit 2 (randomization)
Height and weight	Visit 1 (screening)
Physical examination	Visit 1 (screening)
Laboratory assessments	Visit 1 (screening)
12-lead ECG	Visit 1 (screening)
Vital signs (blood pressure and heart rate)	Visit 2 (randomization)

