5.1. Inclusion Criteria

Participants are eligible to be included in the study only if all of the following criteria apply:

Age

1. Participant must be older than 60 years of age, at the time of signing the informed consent.

Type of Participant and Disease Characteristics

2. Recently (within 6 months) discharged from hospital with a diagnosis of acute exacerbation of COPD (usually coded as DRG 087 or DRG 088).
3. Participants with a clinical diagnosis of COPD (i.e. previous diagnosis of COPD and/or treatment with short acting bronchodilators (SABD), LABD or LABD+ICS
4. Spirometry confirmed diagnosis of COPD, post-bronchodilator (30 minutes after 400 µg salbutamol) FEV1/FVC ratio <0.7. The diagnostic spirometry test can have been performed up to three years prior to randomisation, or if never performed before, should be performed not earlier than 4 weeks since last exacerbation
5. Smokers or ex-smokers with a smoking history of >10 pack years (a pack year is defined as 20 cigarettes smoked every day for a year)
6. Clinical diagnosis documented in the patient's medical records of one or more major chronic cardiac disease (heart failure, ischaemic heart disease or atrial fibrillation).
7. Currently receiving at least one of the specified treatments (either alone or in combination, see Appendix 10.5) for heart failure, ischemic heart disease or atrial fibrillation.
8. Participant must be willing and able to perform pulmonary function tests

Sex

9. Male or female. Contraception is not considered necessary in this cohort of elderly (> 60 years) patients receiving treatment with commercially available licensed products.

Informed Consent

10. Capable of giving signed informed consent as described in Appendix 1 which includes compliance with the requirements and restrictions listed in the informed consent form (ICF) and in this protocol.

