In order to identify suitable participants, investigators at each centre will screen the medical records of all patients hospitalized in their department during the 6 month period before the beginning of the study, who were discharged with a diagnosis of pulmonary oedema/respiratory failure (usually, but not limited to DRG 087 or DRG 088).

Potential participants identified through this search of the medical records will be contacted by the research staff in person or over the phone to ascertain if they are eligible and whether they are interested in participating in the study. If the potential participant is eligible and willing to take part, the investigator or the research staff member will provide a copy of the informed consent form (ICF) for the potential participant to review or will proceed to schedule a time for the participant to come to the clinic to review the informed consent and for the screening visit (Visit 1).

Visit 1: Screening

Eligibility to participate will be assessed from the study inclusion and exclusion criteria.

Eligible participants will be asked to read the Participant Information Sheet and ICF. The participant will be given time to ask questions. Signed informed consent must be obtained from each participant before any study specific procedures are initiated. A copy of the signed consent form and the Participant Information Sheet will be given to each participant to keep.

Participants will be asked to complete both the CAT and mMRC dyspnoea scale questionnaires.

The participant's demography and medical history (including drug, alcohol, tobacco, and caffeine usage) will be recorded.

A physical examination including height and weight will be performed.

Past and current medical conditions, including the participant's history of COPD and the presence of concomitant cardiovascular diseases (in particular HF, IHD and AF) and all related treatment

will be recorded. To be eligible for recruitment into the study the participant must be receiving at least one of the CV treatments specified in Appendix 10.5.

Information about any moderate/severe exacerbations of COPD in the previous year, in addition to the index severe exacerbation, should also be recorded on the eCRF. This information should be assessed from the participant's clinical records and prescription history.

A blood sample will be taken for measurement of baseline laboratory parameters as described in Appendix 2.

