10.2. Appendix 2: Clinical Laboratory Tests

The following blood tests will be performed for screening purposes only at the local hospital laboratory.

- full blood count (to include hemoglobin, hematocrit, mean corpuscular volume (MCV), mean corpuscular hemoglobin (MCH), mean corpuscular hemoglobin concentration (MCHC), red blood cell (RBC) count, white blood cell (WBC) count and differential (platelets, neutrophils, lymphocytes, monocytes, eosinophils and basophils)
- fibrinogen
- NT-BNP or B-type natriuretic peptide (BNP)
- lipid profile (to include total cholesterol, high density lipoprotein (HDL) cholesterol, low density lipoprotein (LDL) cholesterol and triglycerides)
- creatinine
- sodium
- potassium
- calcium
- glucose
- C- reactive protein (CRP)
- alanine amino transferase (ALT)
- gamma glutamyl transferase

*

10.3. Appendix 3: Adverse Events: Definitions and Procedures for Recording, Evaluating, Follow-up, and Reporting

Adverse event (AE) definition

AE Definition

 • An AE is any untoward medical occurrence in a patient or clinical study participant, temporally associated with the use of study intervention, whether or not considered related to the study intervention. • An AE can therefore be any unfavorable and unintended sign (including an abnormal laboratory finding), symptom, or disease (new or exacerbated) temporally associated with the use of study intervention.

Serious adverse event (SAE) definition

A SAE is defined as any untoward medical occurrence that, at any dose:

a. Results in death

b. Is life-threatening
 
The term 'life-threatening' in the definition of 'serious' refers to an event in which the participant was at risk of death at the time of the event. It does not refer to an event, which hypothetically might have caused death, if it were more severe.

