3.3 Sample size justification

The sample size calculation is based on the superiority criteria of the LABD+ICS group versus LABD alone group in terms of re-hospitalization and/or death. With 464 patients in each group, the percentage of patients experiencing the composite event (re-hospitalization and/or death) is expected to be 9% in the LABD+ICS group and 15% in the LABD alone group. A log-rank test (two-sided 5% significance level) will have 80% power to detect a difference between treatment groups in terms of time to first re-hospitalization and/or death (primary efficacy endpoint). Adjusting for an expected 10% dropout rate, a total of 516 patients per group will need to be randomized.

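### No analysis by ICS use at entry is prespecified, so the trial cannot separate the effect of adding ICS from that of stopping it

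*SAP*

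**What the plan says.** - **Eligibility.** Inclusion criterion 3 (Protocol 5.1) accepts a clinical diagnosis of COPD shown by an earlier diagnosis and/or "treatment with short acting bronchodilators (SABD), LABD or LABD+ICS". A patient may enter on ICS or off it.
- **Randomisation.** Centre is the only stratifying factor (Protocol 6.3, SAP 3.4).
- **Primary test.** SAP 7.1 decides the trial on a log-rank test stratified by centre. No other covariate enters it, not even age.
- **Models.** The Cox and Poisson models "will include center and treatment group as qualitative independent variables and age as quantitative independent variable" (SAP 4.4). The ANCOVA models also carry the baseline value of the outcome.
- **Open clause.** SAP 7.1 and Protocol 9.4.6 let further confounders into the Cox model after a Data Review that looks at their balance between arms. No factors are listed, and SAP 4.9 places the meeting after database lock. The Poisson section (SAP 7.2) has no such clause.
- **Subgroups.** SAP 4.3 defines one, by treatment given: LAMA+LABA with or without ICS. Beyond that, "Other subgroup analyses may be performed during post-hoc analyses for efficacy and safety endpoints based on baseline disease characteristics".
- **Data available.** Protocol 6.5 requires medication taken at enrolment to be recorded with dates. At Visit 1 (Protocol section 8) the eCRF is to hold "Information about any moderate/severe exacerbations of COPD in the previous year", apart from the index event. The screening blood count includes "platelets, neutrophils, lymphocytes, monocytes, eosinophils and basophils" (Protocol Appendix 2).

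**The concern.** For a patient on ICS at entry (a prior user), allocation to LABD alone means stopping ICS, and allocation to LABD+ICS means carrying on. For a non-user, LABD+ICS means starting ICS, and LABD alone means no change in ICS. These are two contrasts, and the plan reports only their average.

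Prior users may well be numerous: the protocol's Introduction calls LABA+ICS the most prescribed treatment in these patients, although it gives no share. The documents also treat the two questions as distinct. The Introduction relies partly on a trial of ICS withdrawal, while SAP 4.3 speaks of the value of adding ICS to LABD as something that optional later subgroups might show.

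Without stratum estimates, a positive result could mean that starting ICS helps or that stopping it harms. A diluted or null result could hide an effect confined to one stratum. If the split is made only after the results are known, it will carry little weight.

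**Working it through.** **1. Inputs from the plan (SAP 3.3).** "With 464 patients in each group", event proportions are "expected to be 9% in the LABD+ICS group and 15% in the LABD alone group", and "A log-rank test (two-sided 5% significance level) will have 80% power to detect a difference between treatment groups".

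**2. The plan's own figure.**
- Implied HR = ln(0.91)/ln(0.85) = 0.580.
- Freedman events = (1.960 + 0.842)² × ((1 + 0.580)/(1 − 0.580))² = 111.3.
- Per arm: 111.3/(0.15 + 0.09) = 463.7, so 464. With dropout: 464/0.90 = 516.

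Both figures reproduce. Expected events are 464 × 0.24 = about 111. Nothing in this point changes the stated sample size.

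**3. What pooling would do.** Assumptions, none from the documents: 12-month risk on LABD alone is 15% in both strata; a share f of patients are prior users; the stratum HRs are as shown.

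Pooled risk on LABD+ICS = f(1 − 0.85^HR_users) + (1 − f)(1 − 0.85^HR_non-users). Pooled HR = ln(1 − pooled risk)/ln(0.85). For HRs 0.58 and 1.0 with f = 0.25, the risk is 0.25 × 0.09 + 0.75 × 0.15 = 0.135, and the HR is ln(0.865)/ln(0.85) = 0.89. Power is Schoenfeld's, at 464 per arm.

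| Prior users | Pooled HR (power), 0.58 v 1.0 | Pooled HR (power), 0.58 v 0.80 |
|---|---|---|
| 25% | 0.89 (10%) | 0.74 (37%) |
| 50% | 0.79 (27%) | 0.69 (53%) |
| 75% | 0.68 (55%) | 0.63 (68%) |

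With HR 0.58 in both strata, power on the same formula is 82%.

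**4. Would a covariate separate the strata?** Simulation of 400 trials of 928 patients, 50% prior users, HRs 0.58 and 1.0:
- treatment only: HR 0.79;
- treatment plus entry ICS as a main effect: HR 0.79;
- treatment, entry ICS and their interaction: HR 0.58 in prior users, 1.01 in non-users.

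Only the interaction, or separate stratum estimates, recovers the two effects.

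**5. Does adjustment add power at the planned rates?** With entry ICS purely prognostic (HR 1.5, 2 or 3) and one treatment effect for all, simulated power without and with the covariate was 82.3% v 83.3%, 80.8% v 81.0%, and 80.3% v 80.5%. The Monte Carlo standard error of each figure is about √(0.8 × 0.2/400) = 2 points, so there is no material gain.

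**6. Precision of the proposed analysis.** For 50% prior users and HRs 0.58 v 1.0, events are 0.5 × 464 × 0.24 = 55.7 in users and 0.5 × 464 × 0.30 = 69.6 in non-users.
- The standard error of the log ratio of HRs is √(4/55.7 + 4/69.6) = 0.360, so interaction power is Φ(0.544/0.360 − 1.96) = 33%. Across 25% to 75% users it is 25% to 33%; for 0.58 v 0.80 it is 11% to 14%.
- Typical stratum 95% CIs: users 0.580 × exp(±1.96 × √(4/55.7)) = 0.34 to 0.98; non-users exp(±1.96 × √(4/69.6)) = 0.63 to 1.60.

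**The case against.** The strongest reply is that the objective compares a year of LABD+ICS with a year of LABD alone in a pragmatic trial, and randomisation makes that average effect valid for whoever is enrolled. This stands. The point concerns interpretation, not bias.

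A reader might infer that the short covariate list causes the mixing. It does not: the mixing comes from eligibility, combined with the lack of any analysis by entry ICS, and step 4 shows that a main effect leaves the pooled HR unchanged. A reader might also expect adjustment to strengthen the trial. At the planned rates it does not (step 5), and the deciding log-rank test would not use the added covariates anyway.

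It can fairly be said that the plan is not closed, since the Cox clause admits other factors and SAP 4.3 allows other subgroups. But the clause lists nothing, selects on observed balance after lock in an open-label trial, and adjusts without estimating effects by stratum. The subgroups are optional and post hoc. The crossover sensitivity analysis in SAP 7.1 deals with switches between treatment groups, so it does not separate patients by ICS use at entry.

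Finally, the interaction will have low power and the stratum effects used here are invented. Both are true. The first is a reason to report estimates with intervals rather than a test; the second is why the table is only an illustration.

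**Conclusion.** The point holds as a gap in prespecification: the plan pools ICS addition and ICS withdrawal and plans no estimate that separates them. The overall comparison and the sample size are sound.

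The size depends on two unknowns, the share of prior users and the difference in effect between strata. In the assumed scenarios the pooled HR lies between 0.63 and 0.89 instead of 0.58, and power between 10% and 68%. If the effect is the same in both strata, nothing is lost. The proposed analysis would not restore power to the primary test; it would show what the pooled figure is made of.

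Two further readings go beyond the documents. The plan requires discharge within six months of entry, but no text shows that the discharge date is an eCRF item, so an adjustment for time since discharge cannot be assumed feasible. Eosinophils are measured, and the protocol names eosinophilia as a ground for adding ICS, but that suggests effect modification; a main-effect term would not examine it.

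**What to change.** Before database lock:

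1. **Define ICS use at entry (yes/no)** from the medication record of Protocol 6.5. The previous/concomitant split in SAP 5.6 will not serve: the first group can include drugs stopped long before entry, and the second can include drugs started after randomisation.
2. **SAP 4.3 and 7.1:** prespecify one treatment-by-entry-ICS analysis of the primary endpoint. Report the HR and 95% CI in each stratum and the interaction estimate with its CI, labelled supportive and not a decision rule.
3. **SAP 4.4, with the model text and code in 7.1 and 7.2:** add entry ICS use and the number of moderate/severe exacerbations in the previous year to the Cox and Poisson models. Replace the open Cox clause with this fixed list.
4. **Leave the primary centre-stratified log-rank test unchanged.**

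The cost is SAP wording; the protocol already requires the data for both added factors. With 39 planned centres the Cox model has 38 + 1 + 1 = 40 coefficients on about 111 expected events. The two covariates make 42, and the interaction model 43. Interaction power stays low, at about 11% to 33% in the scenarios above.
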